APPENDIX 3 TIME TO LOSS OF VIROLOGIC RESPONSE

This appendix describes the Time to Loss of Virologic Response (TLOVR) algorithm for analyses at Week 24, 48 and 96. The instructions that follow are based on the FDA guidance from 2002⁶. Guidance from the European Union⁷ indicates that snapshot analyses should be supplemented by at TLOVR analysis.

For this study, the TLOVR analyses are done on the mITT data sets. The assay limit used in the TLOVR analysis is the limit of detection.

TLOVR has two components, a time-to-failure (life table) analysis, and a tabulation of treatment outcomes at each particular time point (e.g. Week 24).

The time to failure data are analyzed using the Kaplan-Meier method. The presentation will include a K-M curve, estimates of the response rates at the end of weeks 24, 48 and 96 and 95% confidence intervals for the estimate. The time-to-failure analysis is based on the following rules (FDA, 2002):

- “For 2 and 3 below, discard all visits with no data. In what follows, visit means visit with an observed viral load. All available visits, including off-schedule visits and post-week 96 visits, should be used for the calculation. Data should not be interpolated for visits or time points with missing data.
- Subjects who never achieved confirmed HIV RNA levels below the assay limit (on two consecutive visits) before any of the following events will be considered to have failed at time 0.
 - a) Death
 - b) Introduction of a new antiretroviral drug to the regimen. Exceptions may be made for certain pre-specified changes in background therapy where the reason for change is due to toxicity or intolerance of background therapy and not the study drug or control.
 - c) Last available visit
- For all subjects who have confirmed HIV RNA levels below an assay limit (two consecutive visits below an assay limit), the time to failure is the earliest of the choices below, with modification specified in 4:
 - a) Time of the event as described in 2b
 - b) Time of loss to follow-up
 - c) Time of confirmed levels above an assay limit. Confirmed is defined as two consecutive visits greater than an assay limit or one visit greater than an assay limit followed by loss to follow-up.
 - d) Time of death
- If the time to virologic failure defined above is immediately preceded by a single missing scheduled visit or multiple consecutive missing scheduled visits, the time of virologic failure is replaced by the time of the first such missing visit.”

The tabulation of treatment outcomes shows the proportions of success and failure for various reasons. For a subject, the reason for failure is based on the primary reason for the earliest treatment failure. For any visit, subjects who achieved confirmed virologic success, defined as two consecutive visits below the assay limit of detection, but have not failed according the above loss of virologic success algorithm are considered successes. All others should be classified into the appropriate categories, which are shown in the FDA draft guidance.

The visit windows used in tabulating treatment outcomes are the same visit windows used for the snapshot algorithm. For subjects who failed for multiple reasons at the earliest time of failure, the precedence of failure classification is: death, virologic rebound and then premature discontinuation. For example, if virologic rebound and premature discontinuation occur on the same day, then the reason for failure is virologic rebound.

APPENDIX 4 EQ-5D-3L SCORING PROGRAM - U.S. WEIGHTED

This SAS scoring algorithm was downloaded on January 20, 2015 from:

<http://archive.ahrq.gov/professionals/clinicians-providers/resources/rice/EQ5Dscore.html>

```
/* EQ-5D U.S. PREFERENCE-WEIGHTED INDEX */
```

```
/* Author: PPD */
```

```
/* Date: May 20, 2004 */
```

```
/* Program was written with SAS Release 8.02 for Windows. */
```

```
/* The scoring algorithm presented below was taken from: Shaw JW, Johnson JA, Coons SJ.  
U.S. Valuation of the EQ-5D Health States: Development and Testing of the D1 Valuation Model.  
Medical Care. Submitted 2004. */
```

```
/* This program computes the U.S. preference-weighted index score using self-reported EQ-5D data.  
It is presumed that the data set includes the following five variables:
```

Dimension	Variable Name	Range
Mobility	MO	1-3
Self-care	SC	1-3
Usual activities	UA	1-3
Pain/discomfort	PD	1-3
Anxiety/depression	AD	1-3

where a 1 indicates no problems, a 2 indicates moderate problems, and a 3 indicates severe problems. The variables containing responses for the five dimensions must be named as above (in capital letters). Missing values should be left blank (ie, a '.' should not be substituted for a missing value). The index score will not be generated when responses are missing for 1 or more of the five dimensions.

In the data step, the user should specify the location (LIBNAME) and name of the data set to be analyzed (DATANAME). It is recommended that the index values be saved to a new data set (NEWDATANAME) in the desired library. */

```
/* SAS Data Step */
```

```
data LIBNAME.DATANAME ; set LIBNAME.NEWDATANAME ;
```

```
/* Generate Dummy Variables for Levels 2 and 3 of Five Dimensions */
```

```
m1 =0 ;  
m2 =0 ;  
s1 =0 ;  
s2 =0 ;  
u1 =0 ;  
u2 =0 ;  
p1 =0 ;  
p2 =0 ;  
a1 =0 ;  
a2 =0 ;
```

```
if MO = 2 then m1 = 1 ;  
if MO = 3 then m2 = 1 ;  
if SC = 2 then s1 = 1 ;  
if SC = 3 then s2 = 1 ;  
if UA = 2 then u1 = 1 ;  
if UA = 3 then u2 = 1 ;  
if PD = 2 then p1 = 1 ;  
if PD = 3 then p2 = 1 ;  
if AD = 2 then a1 = 1 ;  
if AD = 3 then a2 = 1 ;
```

```
/* Generate Interaction Terms (I2, I2-squared, I3, I3-squared) */
```

```
m0 = 0 ;  
s0 = 0 ;  
u0 = 0 ;  
p0 = 0 ;  
a0 = 0 ;
```

```
if m1 = 0 and m2 = 0 then m0 = 1 ;  
if s1 = 0 and s2 = 0 then s0 = 1 ;  
if u1 = 0 and u2 = 0 then u0 = 1 ;  
if p1 = 0 and p2 = 0 then p0 = 1 ;  
if a1 = 0 and a2 = 0 then a0 = 1 ;
```

```
i2 = m1 + s1 + u1 + p1 + a1 ;  
i2 = i2 - 1 ;  
if i2<0 then i2 = 0 ;  
i22 = i2*i2 ;
```

```
i3 = m2 + s2 + u2 + p2 + a2 ;  
i3 = i3 - 1 ;  
if i3<0 then i3 = 0 ;  
i32 = i3*i3 ;
```

```
/* Generate D1 Term */
```

```
i1 = m0 + s0 + u0 + p0 + a0 ;  
d1 = 4 - i1 ;  
if d1<0 then d1 = 0 ;
```

```
/* Generate Raw Index Score */  
pred = .146016*m1 + .557685*m2 + .1753425*s1 + .4711896*s2 + .1397295*u1 + .3742594*u2 + .1728907*p1 + .5371011*p2 + .156223*a1 +  
.4501876*a2 + -.1395949*d1 + .0106868*i22 + -.1215579*i3 + -.0147963*i32 ;  
EQ_index = 1 - pred ;  
if (MO = .) or (SC = .) or (UA = .) or (PD = .) or (AD = .) then EQ_index = . ;/* Drop Variables Generated by Program */  
  
drop m1 m2 s1 s2 u1 u2 p1 p2 a1 a2 m0 s0 u0 p0 a0 i2 i22 i3 i32 d1 pred nvector ;  
run ;
```

APPENDIX 5 EQ-5D-3L SCORING PROGRAM - U.K. WEIGHTED

The following SAS code is an example of computing UK centric utility scores. The code was taken from the BMS SAP for study CN162-007².

```
utility = 1;
if mobility=1 then mob=0;
else if mobility=2 then mob=-0.069;
else if mobility=3 then mob=-0.314;

if selfcare=1 then self=0;
else if selfcare=2 then self=-0.104;
else if selfcare=3 then self=-0.214;

if usualact=1 then usual=0;
else if usualact=2 then usual=-0.036;
else if usualact=3 then usual=-0.094;

if paindis=1 then pain=0;
else if paindis=2 then pain=-0.123;
else if paindis=3 then pain=-0.386;

if anxdep=1 then anxiety=0;
else if anxdep=2 then anxiety=-0.071;
else if anxdep=3 then anxiety=-0.236;

utility = utility + mob + self + usual + pain + anxiety;

if mobility in (2,3) or selfcare in (2,3) or usualact in (2,3) or paindis in (2,3) or anxdep in (2,3)
then utility = utility - 0.081;

if mobility=3 or selfcare=3 or usualact=3 or paindis=3 or anxdep=3 then utility = utility -0.269;
```

11 DOCUMENT HISTORY

Table 11-1: Document History

Version Number	Author(s)	Description
1.0	PPD	Original version Section 1: update schedule of analyses Section 2.4: add protocol amendment 6 Section 7.2: add relevant protocol deviation related to screening eGFR Section 7.3.2.4: add baseline resistance summaries for treated subjects that are identified as protocol defined virologic failures.
2.0	PPD	Section 7.5.2.5: Include summary for newly emergent phenotypic resistance to BMS-955176. For Gag: add summaries by HIV subtype. Section 7.8: was added to describe the integrated outputs Section 8.1: correct visit window for Weeks 16 and 24, and remove Week 20 Section 9: describe content of the reports in more detail Update Table 10-1 based on 2014 IAS-USA

1. CHRONOLOGY

15-OCT-2016 Reporting and Analysis Plan for Study AI468048, Version 2.0
09-NOV-2017 Appendix of Analysis Plan for Study AI468048 (Final Analysis)

2. FINAL ANALYSIS

Per the company decision to end this study prior to all subjects reaching the primary endpoint, a simplified approach for the final report has been proposed by the project team. Hence the final analyses for AI468048 study as described in this appendix will be performed on subjects who were enrolled into this study, regardless of study stage, and will supersede what have been previously stated in the finalized BMS RAP Version 2.0. In addition, due to the GCP non-compliance of Site $\frac{PP}{D}$ ([name] in Chile) with ICH GCP E6 (R2) Guidelines, data obtained from this GCP non-compliant site will not be included in the final analyses (e.g., summary tables of selected efficacy and safety data); however, subject data listings will include all subjects enrolled in this study. Subject data listings for the GCP non-compliant Site $\frac{PP}{D}$ will also be provided.

The details of the final reporting and analysis plan are described as below:

1) Analysis Populations

Due to the GCP non-compliance of Site $\frac{PP}{D}$ data obtained from this GCP non-compliant site will be excluded in the final analyses.

Populations for Analyses for this synoptic report are defined as follows:

- Enrolled subjects are those who signed an informed consent form and were assigned a Patient Identification number (PID).
- Randomized subjects are enrolled subjects who received a treatment assignment from the IVRS and will be used in subject data listings as specified.
- Modified Randomized Subjects are enrolled subjects who received a treatment assignment from the IVRS, excluding subjects from Site $\frac{PP}{D}$. The modified randomized subjects will be used to assess subject disposition.
- Treated Subjects are randomized subjects who received at least 1 dose of study therapy and will be used in subject data listings as specified.
- Modified Treated Subjects are randomized subjects who received at least 1 dose of study therapy, exclude subjects from Site $\frac{PP}{D}$. Modified treated subjects will be used to assess demography and baseline characteristics,

protocol deviations, exposure, concomitant medication, efficacy, resistance and safety data.

- Pharmacokinetic (PK) population is defined as all treated subjects who have any available concentration-time data. The evaluable PK population is a sub-population including all treated subjects who have adequate PK profiles.

2) Demographic and baseline characteristic

This report includes the analyses of demographics, baseline characteristics, and baseline resistance data based on Modified Treated Subjects population. Subject data listings will be based on Treated Subjects population.

The detailed outputs for demographic and baseline characteristic data are listed in the Section 3.1 of List of Displays for Study Population.

3) Simplified report on primary efficacy endpoint

Selected summaries and analyses on primary efficacy endpoint will be performed for this final analysis, based on Modified Treated Subjects population. Subject data listings will be based on Treated Subjects population.

The detailed outputs for primary efficacy endpoint data are listed in the Section 3.2 of List of Displays for Efficacy.

4) Secondary and Exploratory Efficacy Endpoints

Analyses for secondary and exploratory efficacy endpoints, including pharmacokinetic and quality of life endpoints, will not be performed except for HIV-1 RNA, CD4+ counts, and drug resistance endpoints (see additional details in Section 3.4, Virology) which are subject to availability of the data and will be analyzed based on Modified Treated Subjects population. There will be no subgroups and no multivariate analysis performed for secondary and exploratory efficacy endpoints for this final analysis. Subject data listings based on Treated Subjects population except PK data which will be based PK population.

The detailed outputs for primary secondary and exploratory efficacy endpoints are listed in the Section 3.2 of List of Displays for Efficacy.

5) Safety displays

Final safety analysis will be summarized based on Modified Treated Subjects population; however, subject data listings will be based on Treated Subjects population. Subject data listings will be based on Treated Subjects population.

The detailed outputs are listed in the Section 3.3 of List of Displays for Safety.

6) Virology

HIV drug resistance data will be summarized based on Modified Treated Subjects population. Subject data listings will be based on Treated Subjects population.

The detailed outputs for HIV drug resistance data are listed in the section of List of Display for Virology.

7) General

The display for TLFs will be based on BMS shells and will not utilize HARP for SAC.

The list of displays has been updated as shown below.

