6.3 Populations for Analyses

Populations for analyses consist of enrolled, randomized and treated subjects:

- Enrolled subjects are those who signed an informed consent form and were assigned a Patient Identification number (PID).
- Randomized subjects are enrolled subjects who received a treatment assignment from the IVRS. The randomized subjects will be used to assess subject disposition.
- Treated subjects (also referred to as mITT analysis set) are randomized subjects who received at least 1 dose of study therapy. The treated subjects will be used to assess demography and baseline characteristics, protocol deviations, exposure, concomitant medication, efficacy, resistance, safety and outcomes research scales.
- PK population is defined as all treated subjects who have any available concentration-time data. The evaluable PK population is a sub-population including all treated subjects who have adequate PK profiles.

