7.6 Safety

Safety endpoints include the frequency of adverse events (AEs), serious adverse events (SAEs), non-serious adverse events, CDC Class C AIDS events, adverse events leading to discontinuations, deaths and other significant adverse events as reported on case report forms. Other safety endpoints include laboratory abnormalities, changes in laboratory parameters, changes in vital signs and physical measurements, and ECGs. Safety endpoints will not be evaluated through a specific analysis week. All safety data available in the database at the time of the lock will be included.

Safety summaries are provided for treated subjects by as-treated treatment arm, unless otherwise specified.

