3.3. Safety

The Modified Treated Subjects population will be used in the safety summaries and analyses. All treated subjects will be used in the data listings. Subject data listings will be based on Treated Subjects population.

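### The final analysis tabulates safety and Week 24 response only without one site's treated subjects, and four event listings drop that site against the appendix's own rule

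*SAP*

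**What the plan says.** Version 2.0 of the plan, section 6.3, uses one set throughout: "The treated subjects will be used to assess demography and baseline characteristics, protocol deviations, exposure, concomitant medication, efficacy, resistance, safety" (and outcomes research). Section 7.6 adds that "All safety data available in the database at the time of the lock will be included".

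The final-analysis appendix, dated 9 November 2017, declares that it supersedes Version 2.0. Section 2 says that "data obtained from this GCP non-compliant site will be excluded in the final analyses" and defines Modified Treated Subjects as the treated subjects without that site. For efficacy: "Selected summaries and analyses on primary efficacy endpoint will be performed for this final analysis, based on Modified Treated Subjects population". For safety: "Final safety analysis will be summarized based on Modified Treated Subjects population; however, subject data listings will be based on Treated Subjects population". Section 3.3 repeats the safety rule: "The Modified Treated Subjects population will be used in the safety summaries and analyses".

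Section 2 also keeps the site visible. Subject listings are to cover everyone enrolled, and separate listings for the site are promised. Treated Subjects remains a defined population, but its stated use is listings only.

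**The concern.** Non-compliance at a site can make its efficacy data unreliable, and setting those data apart is a defensible choice. It does not undo exposure. When the site's subjects leave both numerator and denominator of the SAE, fatal SAE, discontinuation and Grade 3-4 tables, the report's tabulated harms no longer cover everyone who took study drug. Table 7.6.1-1 of Version 2.0 marks the fatal SAE summaries as registry reporting items, so the reduced counts could be the ones made public.

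For Week 24 response the stake is smaller. A reader of the tables sees one estimate per arm and no companion estimate showing whether it depends on the exclusion. The appendix is dated about 13 months after sites were told of termination (10 October 2016, footnote to Tables 2.2-2.4), in an open-label study. A parallel run is the usual safeguard for a post-randomisation exclusion written down that late.

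**Working it through.** **Step 1. Which population each display uses** (appendix sections 3.1 to 3.3).

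- Week 24 snapshot response, Table 2.1: Modified Treated.
- Tables 2.2-2.4: titled Modified Treated (Observed). Their footnote builds the set from the Treated population and does not name the site exclusion, so their content is unclear.
- Safety summaries, including 3.7 (overall AEs), 3.8 (SAEs), 3.9 and 3.10 (fatal SAEs), 3.13 (AEs leading to discontinuation), 3.18 (Grade 3-4 AEs) and 3.27 (Grade 3-4 laboratory toxicity): Modified Treated.
- Listings with the site in: 7 (snapshot outcomes), 9 and 10 (AEs), 11-22 (laboratory), all on Treated Subjects; deaths (3.12) on Enrolled Subjects.
- Listings with the site out: 3.11 (SAEs), 3.14 (AEs leading to discontinuation), 3.23 (CDC Class C events), 3.25 (gastrointestinal events).

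No summary is listed on Treated Subjects. The last group contradicts the listing rule in section 2, item 5, and in section 3.3. It also departs from the source shells: in the Data Presentation Plan the SAE listing (S.6.2.1E) is on Enrolled Subjects and the other three (S.6.3.1C, S.6.4.1B, S.6.4.1D) are on Treated Subjects. One visible result is that a fatal SAE at the site would appear in listing 3.12 but not in Table 3.9 or listing 3.11.

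**Step 2. The plan's own precision figure.** Version 2.0, section 5, expects about 80% response with 40 per arm and gives roughly 64% to 91%. The exact Clopper-Pearson interval for 32/40 is 64.4% to 90.9%, which agrees.

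**Step 3. Possible shift in response.** The number excluded per arm, k, is not given and is assumed here. From 32/40 (80.0%), the estimate after exclusion lies between (32−k)/(40−k), if all removed were responders, and 32/(40−k), if none were.

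- k = 1: 31/39 = 79.5% to 32/39 = 82.1%
- k = 2: 30/38 = 78.9% to 32/38 = 84.2%
- k = 3: 29/37 = 78.4% to 32/37 = 86.5%
- k = 5: 27/35 = 77.1% to 32/35 = 91.4%

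If the site's subjects resembled the rest of the arm, the upper ends would be unlikely: C(8,2)/C(40,2) = 28/780 = 3.6% for k = 2, and C(8,5)/C(40,5) = 56/658,008 = 0.009% for k = 5.

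**Step 4. Possible loss of harms.** With an assumed event rate p, the chance that at least one affected subject leaves an arm's count is 1−(1−p)^k.

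- p = 5%: 9.8% for k = 2, 18.5% for k = 4
- p = 10%: 19.0% for k = 2, 34.4% for k = 4

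The extreme case is 2 events in 40 (5.0%, exact 95% CI 0.6% to 16.9%), both at the site, so that the table shows 0/38. If the site were like the rest, that has probability 1/780 = 0.13% for k = 2; for k = 5 (0/35) it is 10/780 = 1.3%.

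**The case against.** The strongest reply is that nothing is hidden. Listing 7 gives each treated subject's Week 24 outcome. The AE listing shell carries event type (AE or SAE), intensity and action taken, including discontinuation of drug. The laboratory shell carries toxicity grades. Deaths are listed for all enrolled. Listing 3 shows subjects excluded from analysis, and Table 1.2 is not restricted to a modified set. In a study planned at about 40 per arm, a reader with the full listings can rebuild most of what the tables omit. This stands, and it defeats any claim that the effect of the exclusion cannot be judged. It does not put the harms back into the counts most readers use. It is also weaker for CDC Class C and special-interest gastrointestinal events, because the AE listing shell has no column marking either.

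A second reply is that listings 3.11, 3.14, 3.23 and 3.25 are numbered among the tables, so the listing rule was not meant for them. They are titled as listings, though, and 3.12 in the same block does include the site.

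A third reply is that this is an estimation study, ended early and reported in simplified form, so no confirmatory conclusion depends on the excluded data. That is fair, and it is why the efficacy part calls only for a sensitivity run.

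Two stronger readings are tempting. A reader might infer from the dates that the site was dropped with outcomes in view. Only the appendix is dated, not the discovery of non-compliance or the decision to exclude; the stated reason is GCP non-compliance, and the rule covers the whole site in every arm. A reader might also treat section 7.6 of Version 2.0 as contradicting the appendix. The appendix expressly supersedes it, so this is a declared change.

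**Conclusion.** The point holds for the summary tables and for four event listings. No planned summary of safety or of the Week 24 snapshot includes the excluded site, and listings 3.11, 3.14, 3.23 and 3.25 omit it against the appendix's own rule. The safety part carries most of the weight. Excluding the site from the main efficacy set is acceptable.

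No size of effect can be stated. The site's enrolment per arm is not given, 40 per arm and 80% response are planning values, and the shifts in Step 3 are bounds. They show only that a few subjects could move an arm's estimate by several points, or remove a rare event from the tables. The change should be made; it does not call the whole report into question.

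**What to change.** - Keep Modified Treated Subjects as the main set.
- Repeat Tables 3.7, 3.8, 3.9, 3.10, 3.13, 3.18 and 3.27 on the already defined Treated Subjects set.
- Repeat Table 2.1 on Treated Subjects as a labelled sensitivity run.
- Put listings 3.11, 3.14, 3.23 and 3.25 on Treated Subjects, as section 2 requires.
- Show Treated and Modified Treated counts per arm in Table 1.2.
- In the footnote to Tables 2.2-2.4, say whether the site is in or out.

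The cost is eight repeat tables (seven safety plus Table 2.1) from the same programs with the population flag changed, and four listings re-run. No new data are needed. The downside is that the repeat tables carry data of doubtful reliability, so each must be labelled as including the non-compliant site.
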